### **3.5.3 Research Evaluations**

**Note:** all samples are to be placed on wet ice and transported to the Thoracic Epigenetics Lab (TEL) within one hour of draw

- Cycles 1 and 2 day 1, prior to infusion: 1 mL of plasma will be obtained, filtered through a 0.22 micron filter (Kit available in TEL) to be saved for future clinical reference as needed
- Pharmacokinetic (PK) studies - See [Appendix 3](#) for details - PK samples will be processed and stored in the TEL and later transported to the NCI, POB, Pharmacology and Experimental Therapeutics Section (PETS). Samples will be drawn on days 1, 2, 4, 7, 8, and 9. (**Note:** Patients who do not live locally will not be required to remain in the area for the day 9 PK sample.)
- Baseline (once) and then day 8 of **every cycle** - Two 10 mL red top tubes and 4 10 mL lavender top tubes for the TEL (Note: these are the only specimens collected at each cycle.)
- Tumor biopsies will be collected once at baseline and again on day 8 of cycle 2 as described in Section [5.2](#).
  - Within two days prior to biopsies: Normal PT/PTT with exception of lupus anticoagulant, platelets  $\geq 75,000/\mu\text{L}$ , peripheral ANC  $\geq 750/\mu\text{L}$

### **3.5.4 Follow-up Evaluations:**

After completion the last treatment cycle (See section [3.4](#) for criteria for retreatment), patients will be monitored weekly until all clinically significant toxicities resolve to less than or equal to grade 1 or baseline as follows:

- Toxicity Evaluation
- Laboratory evaluation: CBC, Chem20 equivalent including ionized calcium\*, PT/PTT
- For patients with stable disease or responding to therapy, the following will be done every 2 months until off study criteria are met:
  - History and physical exam
  - Laboratory evaluation: CBC, Chem20 equivalent including ionized calcium\*, PT/PTT
  - Tumor Measurements: CT scan of the chest, abdomen and pelvis as well as PET/CT and brain MR or CT scan.

Note: The patient may have evaluations and lab work obtained through his or her local physician during follow up.

\* Ionized calcium is not part of a standard lab panel and could be omitted if not available or not covered by insurance when performed outside NIH.

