#### **1.3.4 Recent Experience with Mithramycin in Adult Oncology Patients at the NCI**

Twelve patients (10 males; 2 females; median age 51y; range 40-72y) with refractory thoracic malignancies (six MPMs, 2 esophageal cancers, two lung cancers, 2 synovial sarcomas) received 6h mithramycin infusions q day x 7, every 28 days. Response rates following two cycles, pharmacokinetics, and systemic toxicities (cycle 1) were evaluated. A total of 20 cycles were administered to 12 patients; all were evaluable for toxicities. No objective responses were observed in 7 patients who were evaluable for treatment responses. No myelosuppression, uncontrollable nausea or vomiting was observed. No patients experienced bleeding. The lack of these toxicities, which have been associated with mithramycin treatment  may be attributable at least in part to higher purity of the current drug relative to what had been used previously.

Eight patients experienced transient, asymptomatic dose-limiting transaminitis following 25mcg/kg/infusions. This toxicity always occurred on day 4 of the infusion. Percutaneous biopsies from three individuals revealed apoptotic hepatocellular death (**Figure 6A**). Four patients (two with MPM) had no hepatotoxicity and tolerated dose escalation to 30 mcg/kg/infusion. Peak and steady state mithramycin levels were 20 and 8nM, respectively, which were not different in patients with or without hepatotoxicity (**Figure 6B**). DMET genotyping revealed that two SNPs (rs2302387 and rs4668115) in genes encoding two related bile transporters (ABCB4 and ABCB11, respectively) were significantly associated with LFT elevations in the 12 patients treated with mithramycin (**Figure 7A** and **Figure 7B**).

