## **3 STUDY IMPLEMENTATION**

### **3.1 STUDY DESIGN**

This study will be conducted as a single site, phase II trial utilizing a Simon Optimal Design. Patients will be analyzed in two cohorts on the basis of primary thoracic malignancy vs. extra-thoracic malignancy metastatic to lungs, pleura or mediastinum. The goal of the study is to determine response rates, pharmacokinetics and molecular responses following 6h mithramycin infusions as a prelude to combinatorial studies as well as protocols utilizing 24h continuous infusions targeting pharmacodynamic endpoints in tumor tissues.

Patients will undergo eligibility evaluation in the Thoracic Surgery Clinic (OP-3). Patients deemed eligible for therapy will sign an informed consent and receive mithramycin as described in Section 3.2. Patients may continue to receive mithramycin as long as they tolerate drug and do not have progressive disease (Section 6.4).

Patients on study will be closely monitored for the development of toxicities using regular physical examinations, blood pressure monitoring, and laboratory evaluations with particular attention to the development of any signs of bleeding. Patients will be admitted to the hospital for the first treatment cycle to allow for close monitoring of toxicities. For subsequent cycles, local patients may receive infusions in the day hospital; patients traveling from out-of-town will be admitted to the hospital. Two weeks (plus 12 or minus 3 days) following each course of therapy (three 21-day cycles) patients will undergo appropriate staging studies to determine response to therapy using RECIST criteria.

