- Tumor Measurements: CT scan of the chest, abdomen and pelvis, brain MR scan as clinically indicated, as well as FDG-PET and other standard-of-practice scans relevant to each patient's malignancy, as well as liver elastography by ultrasound will be performed two weeks (plus 12 or minus 3 days) after every course of therapy (three cycles).

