### **3.6 CRITERIA FOR REMOVAL FROM PROTOCOL THERAPY AND OFF STUDY CRITERIA**

#### **3.6.1 Criteria for removal from protocol therapy**

- Patient refusal of further treatments
- It is deemed in the best interest of the patient.
- A patient who develops a concurrent serious medical condition that might preclude or contraindicate the further administration of mithramycin will be removed from treatment.
- A patient who becomes pregnant will be immediately taken off therapy.
- Excessive toxicity

**Note:** Patient will be followed until toxicity resolves to baseline or grade 1 or less.

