**Progressive Disease (PD)**

Appearance of one or more new lesions and/or *unequivocal progression* of existing non-target lesions. *Unequivocal progression* should not normally trump target lesion status. It must be representative of overall disease status change, not a single lesion increase.

Although a clear progression of “non-target” lesions only is exceptional, the opinion of the treating physician should prevail in such circumstances, and the progression status should be confirmed at a later time by the review panel (or Principal Investigator).

c. Evaluation of Best Overall Response

The best overall response is the best response recorded from the start of the treatment until disease progression/recurrence (taking as reference for progressive disease the smallest measurements recorded since the treatment started). The patient's best response assignment will depend on the achievement of both measurement and confirmation criteria.

Target Lesions	Non-Target Lesions	New Lesions	Overall Response	Best Overall Response when Confirmation is Required*
CR	CR	No	CR	≥4 wks. Confirmation**
CR	Non-CR Non-PD	No	PR	≥4 wks. Confirmation**
CR	Not evaluated	No	PR	
PR	Non-CR Non-PD Not evaluated	No	PR	
SD	Non-CR Non-PD Not evaluated	No	SD	Documented at least once ≥4 wks. from baseline**

Target Lesions	Non-Target Lesions	New Lesions	Overall Response	Best Overall Response when Confirmation is Required*
PD	Any	Yes or No	PD	No prior SD, PR or CR
Any	PD***	Yes or No	PD	
Any	Any	Yes	PD	

*See RECIST 1.1 manuscript for further details on what is evidence of a new lesion.  **Only for non-randomized trials with response as primary endpoint.  ***In exceptional circumstances, unequivocal progression in non-target lesions may be accepted as disease progression
				

- d. Patients with a global deterioration of health status requiring discontinuation of treatment without objective evidence of disease progression at that time should be reported as “*symptomatic deterioration.*” Every effort should be made to document the objective progression even after discontinuation of treatment.
- e. In some circumstances, it may be difficult to distinguish residual disease from normal tissue. When the evaluation of complete response depends on this determination, it is recommended that the residual lesions be investigated (fine needle aspirate/biopsy) before confirming the complete response status.

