## 8.1 METHODS OF ANALYSIS

Patients who are considered evaluable for response will be included in an analysis of time to progression. Time to progression will be estimated using the product-limit method of Kaplan and Meier. The probability of progression free survival at 6 months will be summarized. Response rates will be calculated as the percent of patients whose best response is a CR or PR, and the fraction of responses obtained will have a 95% confidence interval, which takes into consideration the two-stage nature of the design. Toxicity information recorded will include the type, severity, time of onset, time of resolution, and the probable association with the study regimen. Tables will be constructed to summarize the observed incidence by severity and type of toxicity.

**Time to progression** will be taken as the number of days from enrollment until: (1) disease progression; (2) death because of treatment complications; (3) resection of measurable tumor; or (4) last patient follow-up whichever is first. Patients will be considered to have experienced a progression event if (1) or (2) occurs. Otherwise, the patient will be considered censored for time to progression.

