13.3.2 Appendix 2: Study Calendar

		Cycles 1 and 2							
Research Eligibility Evaluation/Baseline		Week 1							Week 2
		day 1	day 2	day 3	day 4	day 5	day 6	day 7	
Mithramycin		x	x	x	x	x	x	x	
Histologic path confirmation	x								
ABCB4 and ABCB11 status	X								
Informed consent	x								
Medical history	x								
Concurrent meds	x								
Physical examination	x	x i							
Performance status	x	x i							
General labs	x	x	x	x	x	x	x	x	xx b
Serum bile acids (total and fractionated)	x	x						x	
Coagulation labs	x				x				x c
Pregnancy test	x								
Cardiac function tests	x								
Imaging studies incl liver Elastograpy by ultrasound	x								
Adverse events		←—————→							
Tumor biopsy	x								
Research labs		x d							x c
PK	x	x df	x df		x df			x df	x g
EKG	X	x d			x d			x d	

		Cycles 3 and beyond*						
		Week 1					Week 2	
		day 1	day 2	day 3	day 4	day 5	day 6	day 7
Mithramycin		x	x	x	x	x	x	x
Histologic path confirmation								
Informed consent								
Medical history								
Concurrent meds								
Physical examination		x i						

**Abbreviated Title:** Mithramycin for Cancer Stem Cells

**Version Date:** 09/14/2018

	Cycles 3 and beyond*							
	Week 1							Week 2
	day 1	day 2	day 3	day 4	day 5	day 6	day 7	
Performance status	x i							
General labs				x h			x	x a
Coagulation labs				x				x c
Serum bile acids (total and fractionated)	x						x	x e (course 1 only)
Pregnancy test								
Cardiac function tests								
Imaging studies including liver elastography by ultrasound								x e
Adverse events								
Tumor biopsy								
Research labs	x d							x c
EKG	x d						x d	
a - once weekly								
b - twice weekly								
c - day 8 of cycle (same as day 1 of week 2)								
d -prior to dosing								
e – two weeks (plus 12 or minus 3 days ) after the end of each course (1 course = 3 cycles)								
f - end of infusion								
g - 24 and 48 hours after day 7 infusion								
h- CBC with differential only								
i – within 4 days prior to the start of each cycle								
*Patients will continue to receive treatment until criteria for removal from protocol or off-study criteria are met (See section 3.6)								

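### Patients who stop before the first restaging have no scheduled tumor assessment, so response and progression are observed by schedule only in those who complete a course

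*Combined protocol and SAP*

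**What the plan says.** **During treatment.** Section 3.5.2 says that tumor imaging "will be performed two weeks (plus 12 or minus 3 days) after every course of therapy (three cycles"). Section 3.1 repeats this: "following each course of therapy (three 21-day cycles) patients will undergo appropriate staging studies to determine response to therapy using RECIST criteria". Footnote e of the study calendar (Appendix 2) carries the same trigger. None of the three lists a scan at early discontinuation or at the end of treatment.

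**After treatment.** Section 3.5.4 gives every patient toxicity and laboratory checks until toxicity resolves. Imaging is narrower: "For patients with stable disease or responding to therapy, the following will be done every 2 months until off study criteria are met". For patients removed from therapy, section 3.6.1 says: "Patient will be followed until toxicity resolves to baseline or grade 1 or less". It names no tumor assessment.

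**Symptomatic deterioration.** Section 6.5.1.1, item d, asks: "Every effort should be made to document the objective progression even after discontinuation of treatment". It sets no date and no imaging method, and it does not cover patients who stop for toxicity or by refusal.

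**Other scan dates.** Section 6.5.1.1 mentions a Day 60 evaluation in its progression definition. Sections 6.5.6 and 6.5.8 speak of restaging around cycle 2. Neither appears in section 3.5.2 or the calendar.

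**Analysis.** Section 8 counts 7 and then 21 evaluable patients per cohort. Section 8.2 makes receipt of a full course a condition of being evaluable for response, and section 8.1 limits time to progression to those patients. Section 8.2 puts a course at 4 cycles and 28 doses; sections 3.1 and 3.2 put it at three cycles. These must be reconciled.

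**The concern.** The follow-up rule presupposes what the scan is meant to establish. A patient who stops in cycle 1, 2 or 3 has no post-baseline assessment, cannot be classed as stable or responding, and so never enters the two-monthly imaging schedule. Once toxicity has resolved, section 3.5.4 schedules nothing further for that patient, and completing follow-up is itself an off-study criterion in section 3.6.2.

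Patients who stop early are unlikely to be a random subset: toxicity and worsening disease are among the reasons for stopping. If their tumors are not measured, a response reached before stopping goes unseen and a progression goes undated. No later choice of denominator can recover either. Response is the primary endpoint, and a cohort closes if none of its first 7 evaluable patients responds, so a few unobserved outcomes can matter.

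**Working it through.** **1. When the first scheduled scan falls.** Three 21-day cycles plus 14 days: 3 x 21 + 14 = day 77. With the window of minus 3 to plus 12 days, this is day 74 to day 89, before any shift from the cycle-start window in section 3.2. A patient who leaves treatment earlier does not meet the trigger as written.

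**2. The plan's own design (section 8).** Inputs: p0 = 0.05, p1 = 0.30, alpha = beta = 0.10; 7 patients, continue with at least 1 response; 21 in total, success with at least 3.

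P(success) = 1 - P(X1 = 0) - P(X1 = 1) P(X2 <= 1) - P(X1 = 2) P(X2 = 0), with X1 ~ Bin(7, p) and X2 ~ Bin(14, p).

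- At p = 0.30: 1 - 0.0824 - 0.2471 x 0.0475 - 0.3177 x 0.0068 = 0.904.
- At p = 0.05: 1 - 0.6983 - 0.2573 x 0.8470 - 0.0406 x 0.4877 = 0.064.
- Early termination at p = 0.05: 0.95^7 = 0.698, which matches the stated 70%.

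The design reproduces. A search for the smallest expected sample size under p0 within these error limits returns the same design.

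**3. Sensitivity to an unscanned share m.** The documents do not give m for the current cohorts, so it is assumed. The only related figure is in section 1.3.4: "No objective responses were observed in 7 patients who were evaluable for treatment responses". With 12 patients treated, 5/12 = 41.7% were not evaluable. That is used as the upper end of the range.

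- Case (a): unscanned patients count as non-responders but would have responded as often as the rest. The observed rate is 0.30 x (1 - m).
- Case (b): unscanned patients are excluded and replaced, and none would have responded. With a true all-treated rate of 5%, the rate among evaluable patients is 0.05/(1 - m).

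| m | (a) observed rate | (a) power | (a) P(0 of 7) | (b) evaluable rate | (b) P(success) |
|---|---|---|---|---|---|
| 0 | 0.300 | 0.904 | 0.082 | 0.050 | 0.064 |
| 10% | 0.270 | 0.864 | 0.110 | 0.056 | 0.082 |
| 20% | 0.240 | 0.809 | 0.146 | 0.062 | 0.107 |
| 30% | 0.210 | 0.735 | 0.192 | 0.071 | 0.143 |
| 41.7% | 0.175 | 0.620 | 0.260 | 0.086 | 0.207 |

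Each case is an extreme. In (a), if early stoppers would not have responded, counting them as non-responders is correct and nothing is misclassified. In (b), if they respond as often as the rest, excluding them does not shift the rate.

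**4. Which case is nearer the plan.** Sections 8 and 8.2 count evaluable patients only, so exclusion, as in (b), is closer than (a). Replacement has a limit: the ceiling of 57 leaves 57 - 12 - 42 = 3 spare patients if both cohorts run to 21.

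**The case against.** The strongest reply is that the schedule is a minimum. A single-site team would often image a patient who comes off treatment, and section 6.5.1.1, item d, tells it to pursue objective progression in patients who deteriorate. Patients who stop after a first restaging already have one assessment, and those then stable or responding are scanned every two months. All of this stands. A reader might infer that early stoppers have no response or progression data at all, or that the protocol contradicts itself on this point. The documents do not support either. The best-effort line and the schedule can both be followed. What is missing is a scheduled, dated assessment.

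A reader might also infer a plain loss of power. As written the plan does not produce one, because patients without a full course are not counted among the 21. Nor are they censored at last contact: the rule "Otherwise, the patient will be considered censored for time to progression" in section 8.1 applies only within the response-evaluable set, so these patients are left out of that analysis altogether.

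Nor can the 5 of 12 be read as patients who went unscanned. Section 1.3.4 gives no reasons, and section 8 calls the same 12 evaluable. That cohort was not selected by genotype, was on 28-day cycles and was assessed after two. Eight of the 12 had the dose-limiting transaminitis that current eligibility is meant to avoid.

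Finally, if early stoppers rarely respond, scanning them will add few responses, particularly as section 6.5.2 requires confirmation at least 4 weeks later. That is fair for response, but it does not help with undated progression.

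**Conclusion.** The point holds in limited form. A patient who stops before the first restaging has no scheduled tumor assessment, and only an untimed best-effort instruction covers symptomatic deterioration. Together with the full-course condition in sections 8.1 and 8.2, this leaves response and time to progression resting on completers.

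The documents fix neither the direction nor the size of the bias. For 10% to 41.7% unscanned, power at a true 30% rate would be 0.864 to 0.620 against 0.904 if these patients counted as non-responders and were as likely to respond as the rest. The chance of success at a true all-treated rate of 5% would be 0.082 to 0.207 against 0.064 if they were replaced and none would respond. These are illustrations, not forecasts, and the upper share is borrowed from an earlier, different cohort. The scheduling gap itself rests on the text alone and needs none of these assumptions.

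**What to change.** - **Sections 3.1 and 3.5.2, Appendix 2:** set restaging by calendar time from cycle 1 day 1 for every treated patient, on the date the planned scan would have fallen, whether or not three cycles were given.
- **Section 3.5.4:** extend tumor measurements to all patients off therapy without documented progression. Continue until progression, new anticancer therapy, withdrawal or another existing off-study criterion, and accept outside scans. The follow-up period referred to in section 3.6.2 should then mean this extended period.
- **Sections 6.5.1.1, 6.5.6 and 6.5.8:** reconcile the Day 60 evaluation, the cycle 2 restaging and the best-effort instruction with that schedule.
- **Sections 8.1 and 8.2:** align them so that these assessments enter the response and time-to-progression analyses of all treated patients, state how a treated patient with no assessment is counted, and reconcile the definition of a course. Without this step the added scans would not reach the analysis.

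The cost is protocol wording plus some imaging that early stoppers are not now scheduled to have. Some will have to return or send outside scans; section 3.5.4 already allows follow-up evaluations through a local physician. No dose or treatment rule changes.

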### **3.6 CRITERIA FOR REMOVAL FROM PROTOCOL THERAPY AND OFF STUDY CRITERIA**

#### **3.6.1 Criteria for removal from protocol therapy**

- Patient refusal of further treatments
- It is deemed in the best interest of the patient.
- A patient who develops a concurrent serious medical condition that might preclude or contraindicate the further administration of mithramycin will be removed from treatment.
- A patient who becomes pregnant will be immediately taken off therapy.
- Excessive toxicity

**Note:** Patient will be followed until toxicity resolves to baseline or grade 1 or less.

#### **3.6.2 Off-Study criteria**

- Voluntary withdrawal for any reason, or noncompliance with protocol requirements
- Completion of the follow up period (See section 3.5.4)
- Progressive disease, unless the patient is being followed for a serious adverse event related to the research. The event must resolve to less than or equal to grade 1 or baseline prior to removing from the study.
- If the investigator determines that it is in the best interest of the patient to discontinue follow up
- Death

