### **Design:**

- Simon Optimal Two Stage Design for Phase II Clinical Trials targeting an objective response rate (RECIST) of 30%.
- Patients will be stratified based on location of primary disease (thoracic vs. extra-thoracic).
- Patients will receive 6 hour infusions of mithramycin at 30 -50 mcg/kg every day for 7 days, every 21 days (1 cycle). Three cycles will constitute one course of therapy. Those patients tolerating 30 mcg/kg infusions during the first cycle will receive subsequent cycles of mithramycin at a dose of 50 mcg/kg using the same infusion schedule.

*Abbreviated Title: Mithramycin for Cancer Stem Cells*

*Version Date: 09/14/2018*

- Following each course of therapy, patients will undergo restaging studies. Patients exhibiting objective response to therapy or stable disease by RECIST criteria will be offered an additional course of therapy.
- Patients exhibiting disease progression will be removed from study.
- Biopsies of index lesions will be obtained at baseline and on day 8 of the second cycle of therapy for analysis of molecular end-points.
- Pharmacokinetics will be assessed during cycle 1 and cycle 2 of the first course of therapy.

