## **6.2 ROUTINE DATA COLLECTION**

Following registration, all adverse events will be described in the source documents, reviewed by the designated research nurse, and captured in C3D.

- During the follow up period (more than 30 days following the last treatment), only those events that are serious, unexpected, and related to the treatment will be captured in C3D.
- All toxicities occurring within 30 days of treatment will be followed until resolution or return to baseline.

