## **7.3 IND SPONSOR REPORTING CRITERIA**

### **7.3.1 Expedited Adverse Event Reporting Criteria to the IND Sponsor**

During the first 30 days after the subject receives investigational agent/intervention, the investigator must immediately report to the sponsor, using the mandatory MedWatch form 3500a or equivalent, any serious adverse event, whether or not considered drug related, including those listed in the protocol or investigator brochure and must include an assessment of whether there is a reasonable possibility that the drug caused the event. For serious adverse events that occur more than 30 days after the last administration of investigational agent/intervention, only report those that have an attribution of at least possibly related to the agent/intervention.

Required timing for reporting per the above guideline:

- Deaths (except death due to progressive disease) must be reported via email within 24 hours. A complete report must be submitted within one business day.
- Other serious adverse events as well as deaths due to progressive disease must be reported within one business day

Events will be submitted to the Center for Cancer Research (CCR) at: [[contact]](mailto:[contact]) and to the CCR PI and study coordinator.

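### Taking patients off study at progression (section 3.6.2) conflicts with the toxicity follow-up and 30-day reporting rules in sections 3.5.4, 6.2 and 7.3.1

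*Combined protocol and SAP*

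**What the plan says.** **Leaving the study.** Among its off-study criteria, section 3.6.2 has: "Progressive disease, unless the patient is being followed for a serious adverse event related to the research". For the excepted case it adds: "The event must resolve to less than or equal to grade 1 or baseline prior to removing from the study". The Design part of the Précis states the rule with no exception: "Patients exhibiting disease progression will be removed from study".

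**Following toxicity.** Section 6.2: "All toxicities occurring within 30 days of treatment will be followed until resolution or return to baseline". This is not limited by seriousness, cause or disease status. Section 3.5.4 says that after the last cycle "patients will be monitored weekly until all clinically significant toxicities resolve to less than or equal to grade 1 or baseline". Its two-monthly visits, for patients with stable or responding disease, run only until an off-study criterion is met.

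**Reporting and database capture.** Section 7.3.1 requires every serious adverse event in the first 30 days to go to the sponsor, related or not. For serious events later than that, the investigator should "only report those that have an attribution of at least possibly related to the agent/intervention". Section 6.2 sets database capture more than 30 days after the last treatment: "only those events that are serious, unexpected, and related to the treatment will be captured in C3D".

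**When progression is looked for.** Section 3.1: "Two weeks (plus 12 or minus 3 days) following each course of therapy (three 21-day cycles) patients will undergo appropriate staging studies".

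**The concern.** The exception in section 3.6.2 needs an event that is both serious and related to the research. The other rules reach further: section 6.2 to all toxicities within 30 days, section 3.5.4 to all clinically significant ones, and section 7.3.1 to unrelated serious events. A patient can therefore meet the off-study rule while still owing follow-up under another section.

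Toxicity is a secondary objective (section 1.1.2), and section 8.1 plans to record time of resolution as well as type and severity. Patients who tolerate cycle 1 move from 30 to 50 mcg/kg (section 3.2), and section 1.3.3 associates systemic toxicity with doses above 30 mcg/kg. Observation cut short at progression would be lost selectively, in progressing patients only.

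The case is not far-fetched. Section 1.3.4 reports asymptomatic dose-limiting transaminase elevation in 8 of the first 12 patients. Such an event need not meet the seriousness definition in section 7.1.5, and section 3.3 itself provides for ALT and AST that have not recovered within 21 days.

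**Working it through.** **1. The rules side by side for a patient who progresses**

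| Situation at or after progression | Section 3.6.2 | Other sections |
|---|---|---|
| Unresolved, non-serious, clinically significant toxicity | Off study | Follow to resolution (6.2); monitor weekly (3.5.4) |
| Serious event judged unrelated, before day 30 | Off study | Report to sponsor (7.3.1) |
| New toxicity after exit, before day 30 | Already off study | Follow to resolution (6.2) |
| Related serious event under follow-up | Stays on study | Consistent |

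Only the last row is free of conflict, and under the Précis that row conflicts too.

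**2. Does leaving the study end follow-up?** Section 3.6.2 keeps the excepted patient on study so that the event can resolve before removal. That clause is needed only if removal would otherwise end follow-up. Section 3.5.4 also ends its two-monthly visits at off-study status. No section says that adverse-event collection continues after a patient goes off study for progression. The note in section 3.6.1 on following toxicity sits under removal from therapy, a list that does not include progression, so it does not clearly apply.

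**3. Timing.** Inputs: seven daily doses per 21-day cycle and three cycles per course (section 3.2); restaging 14 days after the course, minus 3 or plus 12 days (section 3.1); a 30-day window from the last dose (section 6.2).

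- Last dose: (3 − 1) × 21 + 7 = day 49.
- Window closes: 49 + 30 = day 79.
- Restaging: end of course + 14 (−3/+12).

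The end of the course can be read as the last dose (day 49) or the end of the third 21-day cycle (3 × 21 = day 63).

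| Course ends | Restaging target (range) | Days since last dose | Permitted days before / on / after day 30 |
|---|---|---|---|
| Day 49 | Day 63 (60–75) | 14 (11–26) | 16 / 0 / 0 |
| Day 63 | Day 77 (74–89) | 28 (25–40) | 5 / 1 / 10 |

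At the target date the window has 79 − 63 = 16 days left on the first reading and 79 − 77 = 2 days on the second. Section 8.2 describes a course as four cycles. The last dose is then day 3 × 21 + 7 = 70 and the window closes on day 100, but the intervals since the last dose are the same.

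**4. Capture after day 30.** Section 7.3.1 reports events that are serious and at least possibly related. C3D under section 6.2 takes those that are serious, related and unexpected. The difference is the related serious event classed as expected. Hepatotoxicity and bleeding are listed effects (section 11.1.2), so late cases could fall in that gap.

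**5. Control on the design.** The plan gives no figure on follow-up to reproduce. Its stated 70% chance of stopping early at a 5% response rate does reproduce: 0.95^7 = 0.698. The two-stage rule has an exact type I error of 0.064 and power of 0.904. None of these depends on the off-study rule.

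**The case against.** The strongest reply is that the duties already stand in sections 3.5.4, 6.2 and 7.3.1, so this is loose wording with little effect on data. Much of that reply limits the size of the point.

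- **Timing.** A reader might infer that exit at progression always falls inside the 30 days. It does not. If the course ends on day 63, 10 of the 16 permitted scan days come after day 30. Section 6.5.6 asks for a confirmatory scan when progression is initially seen, unless clinically not indicated, which may delay the call, and progression found at a two-monthly visit may also come later. The Day 60 evaluation in section 6.5.1.1 matches only the earliest edge of the day-49 reading, which is weak support for it.
- **Number affected.** A reader might infer that most patients leave this way. Section 1.3.4 reports no objective responses in 7 evaluable patients but gives no count of progressions, and stable disease continues on treatment.
- **Under-counted toxicity.** Section 1.3.4 says that transaminase elevation always appeared on day 4 of dosing and was transient; section 1.3.3 puts bleeding at around day 4. Section 3.5.2 has toxicity assessed daily or twice weekly during dosing and weekly afterwards. Onset and severity of these main toxicities should be captured before any scan.
- **Seriousness.** Section 7.1.5 includes prolonged hospitalization and important medical events, so some liver events could qualify for the exception.
- **Database gap.** Late related serious events still reach the sponsor, and serious events enter the IRB summary (section 7.2.2), so they are not lost to oversight. An event beyond its listed specificity or severity counts as unexpected (section 7.1.3) and would be captured.

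What does not stand is the claim that the rules agree. The wording of the exception in section 3.6.2 shows that removal ends follow-up, and that rule is narrower than the other three.

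**Conclusion.** The conflict is in the text and does not depend on the timing. A patient who progresses with unresolved non-serious toxicity, or has an unrelated serious event before day 30, is under incompatible instructions. Timing shows that this can arise in ordinary conduct: at the target restaging date, exit comes 14 or 28 days after the last dose, before the window closes on either reading. That arithmetic assumes a completed course and progression called at the first restaging without waiting for confirmation.

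The likely loss is time to resolution, together with late events, in progressing patients. The documents do not allow the number of patients or events to be estimated. Toxicity is a descriptive secondary objective; the response endpoint, sample size, stopping boundaries and error rates are unaffected. The C3D mismatch is separate and smaller: a late related serious event classed as expected reaches the sponsor but not the study database. This should be fixed, but it is not a condition for the trial's primary analysis to be valid.

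**What to change.** Reconcile the Précis and sections 3.5.4, 3.6.2, 6.2 and 7.3.1 so that going off study for progression does not end the 30-day adverse-event collection or the toxicity follow-up that sections 3.5.4 and 6.2 already require. This can be done in the off-study and data-capture wording alone. It needs no change to the reasons for stopping treatment, and it works on either reading of when a course ends. In section 6.2, delete *unexpected* from the rule for events after 30 days, so that C3D holds the same related serious events that section 7.3.1 sends to the sponsor.

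The cost is amendment wording, plus one further contact and local laboratory tests for some progressing patients; section 3.5.4 already allows local laboratories. Some late events will overlap with next-line therapy and be harder to attribute.
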